5.5.12.1.1. Adverse Events

Treatment-emergent adverse events are defined as the reported AEs that first occurred or worsened during the post-baseline phase compared with baseline phase. For each TEAE, the severity level of the event (mild, moderate, or severe) will be determined by patient or physician opinion. The MedDRA Lowest Level Term (LLT) will be used in the treatment emergent computation. For each LLT, the maximum severity at baseline will be used as the baseline severity. If the maximum severity during post-baseline is greater than the maximum baseline severity, the event is considered to be treatment emergent for the specific post-baseline period. For each patient and TEAE, the maximum severity for the MedDRA level being displayed (PT, High Level Term, or SOC) is the maximum post-baseline severity observed from all associated LLTs mapping to that MedDRA level.

For events that are gender-specific, the denominator and computation of the percentage will include only patients from the specific gender.

Adverse event leading to discontinuation will also be summarized.

5.5.12.1.1.1. Potential Hypersensitivity Events

Potential hypersensitivity events (immediate and nonimmediate) will be identified from a review of preferred terms generated from the following queries:

- Anaphylactic reaction Standard MedDRA Query (SMQ)(20000021)
- Broad and narrow terms in the Angioedema SMQ (20000024)
- Broad and narrow terms in the Hypersensitivity SMQ(20000214)

A listing of patients having an event identified from these analyses will be medically reviewed to determine if the terms identified represent actual hypersensitivity events. Listings should include information on timing of event relative to last administered dose of study drug, the event term from this query, other AEs for the patient and timing, any abnormal laboratory findings, medical history, and anti-drug antibody test results including titer. Only those that are judged medically to be hypersensitivity events will be included in the final tables.

The number and percentage of patients with TEAEs, SAEs, and AEs resulting in study drug discontinuation will be summarized by treatment groups using MedDRA PT nested within the SMQ. Events will be ordered by decreasing frequency within the SMQ.

The number and percentage of patients with treatment-emergent hypersensitivity events by maximum severity will be summarized by treatment groups using MedDRA PT.

The number and percentage of patients with TEAEs hypersensitivity events by timing will be summarized using MedDRA PT nested within the SMQ. Events will be ordered by decreasing frequency. Note the timing of the hypersensitivity events is collected through eCRF and categorized into the following four categories:

- Occurs within minutes (<60 minutes) of study drug administration
- Occurs from 1 up to 6 hours of study drug administration
- Occurs from >6 hours through 14 days from study drug administration, which will be split into two categories: on the same day of injection and after the day of injection
- Occurs >14 days of study drug administration

The relationship between the development of TEAE of hypersensitivity events and treatmentemergent ADA within LY2951742 dose groups will be examined.

5.5.12.1.1.2. Adverse Events Related to Injection Sites

Adverse events related to injection sites will be defined using terms from the MedDRA High Level Term "Injection Site Reactions".

The number and percentage of patients with TEAEs related to injection sites, SAEs related to injection sites, and AEs related to injection sites resulting in study drug discontinuation will be summarized using MedDRA PT nested within the High Level Term. Events will be ordered by decreasing frequency within High Level Term.

The number and percentage of patients with TEAEs related to injection sites by maximum severity will be summarized by treatment groups using MedDRA PT nested within the High Level Term. For each patient and AEs related to injection sites, the maximum severity for the MedDRA level being displayed (PT) is the maximum post-baseline severity observed from all associated LLTs mapping to that MedDRA level.

The number and percentage of patients with TEAEs related to injection sites by timing will be summarized using MedDRA preferred terms ordered by decreasing frequency. Note the timing of AEs related to injection sites is collected through eCRF and categorized into the same categories as for hypersensitivity events.

The relationship between the development of TEAEs related to injection sites and TEAEs of hypersensitivity events will be explored for all treatment groups. Additionally, the relationship between the development of TEAEs related to injection sites and treatment emergent ADA will be explored for LY2951742 group.

5.5.12.1.1.3. Upper Respiratory Tract Infections

Upper respiratory tract infections will be defined using all the PTs from the 2 high level terms of "upper respiratory tract infections" and "upper respiratory tract infections NEC" as defined in MedDRA.

The number and percentage of patients with TEAEs of upper respiratory tract infections will be summarized by treatment group using MedDRA PTs. Events will be ordered by decreasing frequency in the pooled LY2951742 group.

The number and percentage of patients with TEAEs of upper respiratory tract infections by maximum severity will be summarized by treatment groups using MedDRA PT. For each patient and upper respiratory tract infection event, the maximum severity for the MedDRA level being displayed (PT) is the maximum post-baseline severity observed from all associated LLTs mapping to that MedDRA level.

By-subject listings of treatment-emergent upper respiratory tract infections, and upper respiratory tract infections leading to study drug discontinuation will be provided.

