5.5.12.1.6. Immunogenicity

To evaluate the changes in immunogenicity data (Anti-LY2951742 Antibody (hereafter "Anti-Drug Antibody (ADA)," Neutralizing ADA (hereafter "Neutralizing Antibody (NAb)") after treatment, the following statistical analyses are planned for comparison between treatment groups.

- The incidence of ADA positive and NAb Positive during baseline.
- The incidence of treatment-emergent ADA (TE ADA) between treatment groups will be summarized for Study Period III. The incidence of TE ADA during Study Periods III and IV combined will be summarized. The baseline and post-baseline definitions for each study period is shown in Table 5.5. Treatment-emergent ADA will be defined as any of the following:
 - o a negative baseline result and a positive post-baseline ADA result with a titer ≥20. This is also called treatment-induced ADA.
 - a positive baseline result and a positive post-baseline ADA result with a ≥4-fold increase in titers (for example, baseline titer of 10 increasing to ≥40 post-baseline).
 This is called treatment-boosted ADA.
- The incidence of TE-ADA and NAb Positive combined between treatment groups will be summarized for the same time periods as planned for the incidence of TE ADA.
- The following will also be created:
 - Listing of subjects with TE ADA at any time during study, NAb Status will also be displayed.
 - Listing of subjects with ADA detected at any time during study, excluding subjects with TE ADA.
 - o Line plot of ADA titers over time for each subject with TE ADA at any time.
 - Listing of subjects with TEAEs for hypersensitivity events or TEAEs related to injection sites for subjects with ADA present at any time.

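### Reviewers who decide which flagged events are hypersensitivity see antibody titres, which can introduce or enlarge the association with antibodies that the SAP examines next

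*SAP*

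**What the plan says.** SAP 5.5.12.1.1.1 (Potential Hypersensitivity Events) works in stages.

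- **Finding candidates.** "Potential hypersensitivity events (immediate and nonimmediate) will be identified from a review of preferred terms generated from the following queries"; the queries are the anaphylactic reaction, angioedema and hypersensitivity SMQs. Antibody status plays no part here.
- **Confirming them.** A patient listing is to be "medically reviewed to determine if the terms identified represent actual hypersensitivity events". It carries six kinds of information: timing relative to the last dose, the event term, other adverse events, abnormal laboratory findings, medical history, and "anti-drug antibody test results including titer".
- **Carrying them forward.** "Only those that are judged medically to be hypersensitivity events will be included in the final tables".
- **Relating them to antibodies.** "The relationship between the development of TEAE of hypersensitivity events and treatmentemergent ADA within LY2951742 dose groups will be examined".

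SAP 5.5.12.1.6 defines TE ADA from the same titres. One route is "a negative baseline result and a positive post-baseline ADA result with a titer ≥20"; the other is a rise of at least 4-fold from a positive baseline.

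The next subsection, 5.5.12.1.1.2, treats injection-site events differently: "Adverse events related to injection sites will be defined using terms from the MedDRA High Level Term" for injection site reactions. They are related to TE ADA without any antibody-informed review in between.

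**The concern.** The event definition and the exposure are not kept apart. A reviewer who is unsure whether a rash or a swelling was a true hypersensitivity reaction may reasonably lean towards yes when the titre is high, and towards no when no antibody was found. Each such decision moves an event into or out of the outcome according to the exposure it will later be set against. The resulting association then partly reflects the review itself.

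This matters because the consequences of anti-drug antibodies are a stated secondary objective (Protocol Table CGAH.1; SAP Table 4.2). Hypersensitivity is one of two adverse event types that the SAP relates to TE ADA. If the table shows an association, a reader cannot tell how much of it came from the classification step.

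**Working it through.** **Figures in the plan.** The documents give no hypersensitivity rate, ADA rate, confirmation rate or association estimate, so there is no planned figure to reproduce. The check is first of the text, then of the mechanism under stated assumptions.

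**Text.** Three things would break the circularity: masking the reviewers to ADA, a first classification made without ADA, or a parallel analysis of all flagged events against TE ADA. None of them appears in the SAP or the protocol. The sentence on the ADA relationship does not repeat that it uses confirmed events only; that follows from the rule on the final tables.

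**Mechanism.** Let *f* be the risk of a flagged event, the same with and without TE ADA (no true association). Let *c1* and *c0* be the probabilities that a flagged event is confirmed in patients with and without TE ADA.

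- Risk of a confirmed event: *a* = *f* × *c1* with TE ADA, *b* = *f* × *c0* without.
- Apparent risk ratio: *a*/*b* = *c1*/*c0*. It does not depend on *f* or on the TE ADA rate.
- Apparent odds ratio: [*a*/(1 − *a*)] / [*b*/(1 − *b*)].

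Example: *f* = 0.10, *c1* = 0.75, *c0* = 0.50 gives *a* = 0.075 and *b* = 0.050. The risk ratio is 1.50 and the odds ratio is (0.075/0.925)/(0.050/0.950) = 1.54.

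**Inputs for the table.** The one document figure is 206 patients per active dose (SAP 5.2), so 206 + 206 = 412 on LY2951742, pooled for the illustration. Everything else is assumed: TE ADA 5% to 10%, flagged events 5% to 10%, and the confirmation probabilities. The last column is the exact chance of a two-sided Fisher p ≤ 0.05, by full enumeration. It is only a yardstick, because the SAP names no test for this relationship.

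| Confirmed, TE ADA vs none | Risk ratio | Odds ratio | Chance of p ≤ 0.05 |
|---|---|---|---|
| 50% vs 50% (ADA masked) | 1.00 | 1.00 | 2.0% to 2.7% |
| 75% vs 50% | 1.50 | 1.52 to 1.54 | 5.0% to 11.2% |
| 100% vs 50% | 2.00 | 2.05 to 2.11 | 9.5% to 26.0% |
| 90% vs 30% | 3.00 | 3.09 to 3.20 | 14.9% to 39.6% |

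A milder tilt from a base of 60% gives 70/60 = 1.17, 80/60 = 1.33 and 90/60 = 1.50.

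**Counts.** At TE ADA 5% there are 21 such patients among 412, and 21 × 0.05 = 1.05 expected flagged events. At 10% for both there are 41 patients and 41 × 0.10 = 4.1 events. With so few events, one or two decisions can change the table. Within a single dose of 206 the counts are about half as large.

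**The case against.** Much can be said for the plan.

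- **ADA is legitimate clinical information.** Protocol 8.4.3 asks for an immunogenicity sample, when possible, after a potential systemic allergic reaction, so the documents treat it as part of the work-up. This stands as a reason for ADA to be seen at some point. It does not require ADA to be seen before the event is classified.
- **ADA is one of six items, and no rule makes it decisive.** This stands. A reader might infer that the plan necessarily manufactures the association. The text supports only that it can, as far as reviewers give weight to ADA.
- **No test is planned.** A reader might take the analysis as a formal hypothesis test. The SAP says only that the relationship will be examined, with no test, effect measure or alpha. Fisher's exact test in 5.5.12.1 is for comparisons between treatment groups. A descriptive table can still mislead.
- **The effect on the arms is not shown.** A reader might infer that titres unblind the review and bias the comparison with placebo. The documents give no ADA rate by arm. They provide for pre-existing ADA in all participants (SAP 5.4.5) and summarise TE ADA between treatment groups (SAP 5.5.12.1.6). Treatment assignment is not among the listed review items, and the ADA relationship is examined only within the active dose groups. A shift is possible if TE ADA is commoner on active drug; more cannot be said.
- **Other outputs limit the harm.** TEAEs are still tabulated by preferred term, system organ class and High Level Term (SAP 5.5.12), so rejected events are not lost. The injection-site analysis is free of the problem, and patient-level ADA listings and titre plots are planned. None of these replaces a relationship analysis with ADA-free event classification.

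**Conclusion.** The circularity is in the text: titres inform confirmation, confirmation decides which events enter the tables, and the events are then related to an exposure built from those titres. The review can introduce or enlarge an association between TE ADA and hypersensitivity to the extent that reviewers weigh ADA. How far they would do so cannot be derived from the documents, so the ratios above illustrate the mechanism and do not estimate the bias.

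The problem is confined to the hypersensitivity tables and their relationship with ADA. Because the analysis is descriptive and serves an other secondary objective without multiplicity adjustment, this is a cheap improvement to make. It is not an error that invalidates the plan.

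**What to change.** In SAP 5.5.12.1.1.1:

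1. Remove ADA results and titre from the listing used to classify flagged events. Keep the other five items, and state that the listing carries no treatment assignment.
2. Add one sentence on order of work: the classification is completed and frozen, and ADA data are merged afterwards for the relationship analysis and the patient listings.
3. If reviewers want ADA as clinical context, run a second, ADA-informed review and label it a sensitivity analysis.
4. Present TE ADA against all SMQ-flagged events beside the table of confirmed events.

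The change belongs in the SAP before unblinding, in line with Protocol 9.2. It costs one listing column, one sentence and one extra table, plus the second review if it is wanted. The downside is slightly less clinical context at the first pass. The listing in SAP 5.5.12.1.6 of hypersensitivity and injection-site events in patients with ADA still brings the two sources together for clinical reading.

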5.5.12.1.2. Suicide-Related Thoughts and Behaviors

Suicidal ideation, suicidal behavior, and self-injurious behavior without suicidal intent occurring during treatment, based on the Columbia-Suicide Severity Rating Scale (C-SSRS), will be summarized by treatment. In particular, for each of the following events, the number and percent of patients with the event will be enumerated by treatment: completed suicide, nonfatal suicide attempt, interrupted attempt, aborted attempt, preparatory acts or behavior, active suicidal ideation with specific plan and intent, active suicidal ideation with some intent to act without

specific plan, active suicidal ideation with any methods (no plan) without intent to act, nonspecific active suicidal thoughts, wish to be dead, and self-injurious behavior without suicidal intent.

In addition, the number and percent of patients who experienced at least 1 of various composite measures during Study Period III and Study Period IV separately will be presented and compared. Composite measures include suicidal behavior (completed suicide, non-fatal suicidal attempts, interrupted attempts, aborted attempts, and preparatory acts or behavior), suicidal ideation [active suicidal ideation with specific plan and intent, active suicidal ideation with some intent to act without specific plan, active suicidal ideation with any methods (no plan) without intent to act, non-specific active suicidal thoughts, and wish to be dead], and suicidal ideation or behavior.

The number and percent of patients who experienced at least 1 of various comparative measures during treatment will be presented and compared for Study Period III and summarized for SP IV. Comparative measures include treatment emergent suicidal ideation compared to recent history, treatment emergent serious suicidal ideation compared to recent history, emergence of serious suicidal ideation compared to recent history, improvement in suicidal ideation at endpoint compared to baseline, and emergence of suicidal behavior compared to all prior history.

Specifically, the following outcomes are C-SSRS categories and have binary responses (yes/no). The categories have been re-ordered from the actual scale to facilitate the definitions of the composite and comparative endpoints, and to enable clarity in the presentation of the results.

Category 1 – Wish to be Dead

Category 2 – Non-specific Active Suicidal Thoughts

Category 3 – Active Suicidal Ideation with Any Methods (Not Plan) without Intent to Act

Category 4 – Active Suicidal Ideation with Some Intent to Act, without Specific Plan

Category 5 – Active Suicidal Ideation with Specific Plan and Intent

Category 6 – Preparatory Acts or Behavior

Category 7 – Aborted Attempt

Category 8 – Interrupted Attempt

Category 9 – Actual Attempt (non-fatal)

Category 10 – Completed Suicide

Self-injurious behavior without suicidal intent is also a C-SSRS outcome (although not suicide-related) and has a binary response (yes/no).

Composite endpoints based on the above categories are defined below.

- Suicidal ideation: A "yes" answer at any time during treatment to any one of the five suicidal ideation questions (Categories 1-5) on the C-SSRS.
- Suicidal behavior: A "yes" answer at any time during treatment to any one of the five suicidal behavior questions (Categories 6-10) on the C-SSRS.

 Suicidal ideation or behavior: A "yes" answer at any time during treatment to any one of the ten suicidal ideation and behavior questions (Categories 1-10) on the C-SSRS.

The following outcome is a numerical score derived from the C-SSRS categories. The score is created at each assessment for each patient and is used for determining treatment emergence.

• Suicidal Ideation Score: The maximum suicidal ideation category (1-5 on the C-SSRS) present at the assessment. Assign a score of 0 if no ideation is present.

For Study Period III and Study Period IV, comparative endpoints of interest are defined below. "Treatment emergence" is used for outcomes that include events that first emerge or worsen. "Emergence" is used for outcomes that include events that first emerge.

- Treatment emergent suicidal ideation compared to recent history:
 An increase in the maximum suicidal ideation score during treatment (Visits 3.01 to 12 for SP III; Visits 12.01 to 14 for SP IV) from the maximum suicidal ideation category during the screening and lead-in periods (C-SSRS scales taken at Visits 1 to 3 excluding "lifetime" for SP III; C-SSRS scales taken at Visits 1 to 12.02 excluding "lifetime" for SP IV). Recent history excludes "lifetime" scores from the Baseline C-SSRS scale or Baseline/Screening C-SSRS scale.
- Treatment-emergent serious suicidal ideation compared to recent history: An increase in the maximum suicidal ideation score to 4 or 5 on the C-SSRS during treatment (Visits 3.01 to 12 for SP III; Visits 12.01 to 14 for SP IV) from not having serious suicidal ideation (scores of 0-3) during the screening and leadin periods (C-SSRS scales taken at Visits 1-3 excluding "lifetime" for SP III; C-SSRS scales taken at Visits 1 to 12 excluding "lifetime" for SP IV). Recent history excludes "lifetime" scores from the Baseline C-SSRS scale or Baseline/Screening C-SSRS scale.
- Emergence of serious suicidal ideation compared to recent history:
 An increase in the maximum suicidal ideation score to 4 or 5 on the C-SSRS during treatment (Visits 3.01 to 12 for SP III; Visits 12.01 to 14 for SP IV) from no suicidal ideation (scores of 0) during the screening and lead-in periods (C-SSRS scales taken at Visits 1 to 3 excluding "lifetime" for SP III; C-SSRS scales taken at Visits 1 to 12 excluding "lifetime" for SP IV). Recent history excludes "lifetime" scores from the Baseline C-SSRS scale or Baseline/Screening C-SSRS scale.
- Improvement in suicidal ideation at endpoint compared to baseline: A decrease in suicidal ideation score at endpoint (the last measurement during treatment; Visits 3.01 to 12 for SP III; the last measurement during open-label phase Visits 12.01 to 14 for SP IV) from the baseline measurement (the measurement taken just prior to treatment Visit 3 for SP III; the last non-missing measure during Visits 3.01 to 12 for SP IV).

• Emergence of suicidal behavior compared to all prior history:
The occurrence of suicidal behavior (Categories 6-10) during treatment (Visits 3.01-12 for SP III; Visits 12.01 to 14 for SP IV) from not having suicidal behavior (Categories 6-10) prior to treatment (Visits 1-3 including "lifetime" for SP III; C-SSRS scales taken at Visits 1 to 12 including "lifetime" for SP IV).

Patients who discontinued from the study with no post-baseline C-SSRS value will be considered unevaluable for analyses of suicide-related events. Only evaluable patients will be considered in the analyses. Fisher's exact test will be used for treatment comparisons. For each event, p-values will only be displayed if at least 4 events occurred in at least 1 treatment group.

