- Immunogenicity, CCl and PK sampling to be performed at the indicated visits and prior to dose administration if the visit is a dosing visit. Samples will be taken in the event of early termination. Immunogenicity samples also may be collected in the event of a systemic allergic/hypersensitivity reaction (see Section 8.4.3). The timing of samples will be recorded.
- k Patients will receive injections of placebo or LY2951742 after all other visit procedures are completed. Following the first dose at Visit 3, patients will be observed for at least 30 minutes in the office.
- 1 Questionnaire administered by clinician to assess other chronic pain conditions.
- m The C-SSRS and SHSF (and SHFU when applicable) will be completed at scheduled and unscheduled office visits.

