Treatment-emergent immunogenicity	Post-treatment population	Visit 3	All Visits 12.01-14		

Patient Population with Baseline and Post-Baseline Definitions by Study Period and Type of Analysis

Study Period/Analysis	Patient Population	Baseline Observation	Post-baseline Observation(s)
Study Period IV			
Treatment-emergent changes in	Post-treatment population with a baseline and at least one	Low:	Low:
temperature and weight	post-baseline observation	Minimum value from	Minimum value from
		Visits 1-12	Visits 12.01-14
		High:	High:
		Maximum value from	Maximum value from
		Visits 1-12	Visits 12.01-14
Treatment-emergent changes in blood	Post-treatment population with a baseline and at least one	Low:	Low:
pressure, pulse and ECGs	post-baseline observation	Last non-missing from	Minimum value from
		Visits 1-12	Visits 12.01-14
		High:	High:
		Last non-missing from	Maximum value from
		Visits 1-12	Visits 12.01-14

Abbreviations: ANCOVA = analysis of covariance; C-SSRS = Columbia Suicide Severity Rating Scale; ECG = electrocardiogram; ITT = intent-to-treat; LOCF = last observation carried forward; NA = not applicable; TEAE = treatment-emergent adverse event.

Note: Visit 3.01 indicates the first unscheduled visit occurring after Visit 3 and prior to Visit 4. Visit 12.01 indicates the first unscheduled visit occurring after Visit 12 and prior to Visit 13.

^a Lifetime is captured in the C-SSRS visit 1 CRF.

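### In one Study Period IV C-SSRS endpoint the baseline window runs to Visit 12.02 and overlaps the post-baseline window, so ideation at the first two unscheduled follow-up visits cannot by itself count as treatment-emergent

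*SAP*

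**What the plan says.** SAP 5.5.12.1.2 lists five comparative C-SSRS endpoints and gives each a baseline and a post-baseline window for Study Periods III and IV.

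The first is treatment-emergent suicidal ideation compared to recent history. Its event rule is "An increase in the maximum suicidal ideation score during treatment", with the post-baseline window for Study Period IV given as "Visits 12.01 to 14 for SP IV". The matching baseline is "C-SSRS scales taken at Visits 1 to 12.02 excluding" lifetime scores.

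The two serious-ideation endpoints use "C-SSRS scales taken at Visits 1 to 12 excluding" lifetime scores. Emergence of suicidal behavior uses "C-SSRS scales taken at Visits 1 to 12 including" lifetime scores. Improvement in ideation uses "the last non-missing measure during Visits 3.01 to 12 for SP IV".

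The note to SAP Table 5.5 fixes the numbering: "Visit 12.01 indicates the first unscheduled visit occurring after Visit 12 and prior to Visit 13". Footnote m to the Schedule of Activities (Protocol Appendix 2) says that the C-SSRS and its companion self-harm form "will be completed at scheduled and unscheduled office visits". SAP 5.5.12.1 brings unscheduled visits into categorical safety analyses unless otherwise specified, and makes Study Period IV descriptive only.

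**The concern.** An endpoint built on change from baseline needs a baseline that closes before the post-baseline window opens. Here the baseline closes two unscheduled visits after that point. New ideation recorded at either visit is treated as history and as outcome at once, and cancels itself.

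Follow-up is there to observe safety during wash-out (Protocol 4.3). Under the Schedule of Activities the C-SSRS is due at Visits 12, 13 and 14, with a target of 60 days from Visit 12 to Visit 13. Unscheduled office visits are therefore the only source of C-SSRS data between those two visits. A programmer following the text would exclude that information from the treatment-emergent ideation count, except as a higher hurdle for later visits.

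**Working it through.** The plan states no figure to reproduce. The check sets the definitions side by side and applies the event rule.

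**Step 1. Study Period IV windows in SAP 5.5.12.1.2**

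| Endpoint | Baseline | Post-baseline | Visits in both |
|---|---|---|---|
| Treatment-emergent ideation | 1 to 12.02 | 12.01 to 14 | 12.01, 12.02 |
| Treatment-emergent serious ideation | 1 to 12 | 12.01 to 14 | none |
| Emergence of serious ideation | 1 to 12 | 12.01 to 14 | none |
| Improvement in ideation | last of 3.01 to 12 | last of 12.01 to 14 | none |
| Emergence of suicidal behavior | 1 to 12 | 12.01 to 14 | none |

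For Study Period III the first endpoint uses Visits 1 to 3 against 3.01 to 12, with no overlap. In Table 5.5 the Study Period IV baselines for adverse events, laboratory values, temperature, weight, blood pressure, pulse and ECGs all end at Visit 12. Table 5.5 lists C-SSRS only under Study Period III, so it does not override the definition in the text.

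**Step 2. The event rule**

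Let B be the maximum score over Visits 1 to 12, U the maximum over Visits 12.01 and 12.02, and L the maximum over all later Study Period IV visits.

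- As written: event if max(U, L) > max(B, U). Since U can never exceed max(B, U), this reduces to L > max(B, U).
- Baseline ending at Visit 12: event if max(U, L) > B.

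As written, U acts only as a hurdle for L. The two rules differ exactly when U > B and L ≤ U, and the as-written rule always gives the lower count.

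**Step 3. Examples, all with B = 0**

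| Score at 12.01 | Later scores | As written | Baseline to Visit 12 |
|---|---|---|---|
| 3 | 0 | not counted | counted |
| 3 | 3 at Visit 13 | not counted | counted |
| 2 | 4 at Visit 13 | counted | counted |
| 4 | 0 | not counted | counted |

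The third patient is counted as written only because of the later worsening. The fourth meets treatment-emergent serious ideation, whose baseline ends at Visit 12, but not treatment-emergent ideation.

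**Step 4. All score patterns**

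Take scores 0 to 5 in five slots: the maximum of Visits 1 to 12, then 12.01, 12.02, 13 and 14. There are 6^5 = 7776 patterns. For a given U = m there are (m+1)² − m² = 2m+1 ways to fill 12.01 and 12.02, and (m+1)² ways to keep Visits 13 and 14 at or below m.

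- With B = 0, U > 0 and L ≤ U: the sum over m = 1 to 5 of (2m+1)(m+1)² = 12 + 45 + 112 + 225 + 396 = 790. As written, 0 of 790 count; with the baseline ending at Visit 12, all 790 do.
- Over all B, each term is multiplied by m, the number of values of B below m: 12 + 90 + 336 + 900 + 1980 = 3318 patterns gain an event under the change, and none lose one.

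These are counts of logical patterns. They show the direction of the error and say nothing about how many patients it affects.

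**Step 5. Who loses every treatment-emergence flag**

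Among patients with U > B and L ≤ U:

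- If U is 4 or 5 and B is 0 to 3, treatment-emergent serious ideation still records the patient. If B = 0, emergence of serious ideation does too.
- If U is 1 to 3, neither serious-ideation endpoint applies.
- If B = 4 and U = 5, neither applies, because both need a baseline below 4.

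The loss therefore falls mainly on patients scoring 1 to 3 at those visits.

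**The case against.** The best defense is that 12.02 is evidently a slip for 12, that it sits in one of five endpoints, and that little depends on it. Much of this stands. The sibling endpoints and the Table 5.5 rows for adverse events, laboratory values, vital signs, weight and ECGs point to Visit 12 as the intended end. The composite suicidal-ideation measure, reported separately for Study Period IV, counts any positive answer and so keeps every affected patient. The comparative measures are only summarized for Study Period IV. Referral of an individual patient under Protocol 8.2.1.2 does not depend on this definition.

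It does not remove the point. Nothing in the SAP corrects the window, and programming follows the text. C-SSRS data at these visits can exist and do enter the analysis, so the rule as written can give a wrong count.

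A reader might infer three stronger things that the documents do not support:

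- That post-treatment ideation disappears from the safety tables. It is lost from one row and kept in others.
- That the serious-ideation count would exceed the ideation count. One patient shows that the endpoints are not nested. The totals reverse only if such patients outnumber those in the ideation row who do not meet the serious endpoint.
- That unscheduled visits are where new symptoms are most likely to be recorded. The documents say only that the C-SSRS is completed there.

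**Conclusion.** The definition is wrong as written and should be corrected, but the consequence is small. It can undercount one descriptive Study Period IV safety row, always in the direction of fewer events, and only for patients with a C-SSRS at Visit 12.01 or 12.02 that exceeds everything before it and is not exceeded later in the period. Primary, key secondary and other efficacy results are unaffected.

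The conclusion assumes that 12.02 is the second unscheduled visit after Visit 12. The SAP defines 12.01 explicitly and leaves 12.02 to be read from the same numbering. The overlap at 12.01 does not need that assumption. The number of patients is unknown, because the documents give neither the frequency of unscheduled follow-up visits nor ideation rates. Since such events may be few, one misclassified patient could change a cell.

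**What to change.** In SAP 5.5.12.1.2, end the Study Period IV baseline for treatment-emergent suicidal ideation at Visit 12 instead of Visit 12.02, still excluding lifetime scores. For consistency, add a Study Period IV row for C-SSRS categorical analyses to Table 5.5, with baseline Visits 1 to 12 and post-baseline Visits 12.01 to 14. Carry over the lifetime rules, and note that the improvement endpoint keeps its own baseline of the last value over Visits 3.01 to 12.

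The cost is one number and one table row. No new data are needed and no other endpoint changes. SAP 5.8.3 places the Study Period IV safety analyses at final database lock, so the correction belongs before those tables are programmed.
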